### 4.1. Overall Design

- Study 200894 is a double-blind, double-dummy, randomized, parallel group, placebo-controlled superiority study. The study will be conducted as a collaboration between the Eijkman Institute of Molecular Biology (Jakarta), Eijkman Oxford Clinical Research Unit (within the Eijkman Institute, Jakarta), Faculty of Medicine, University of Indonesia (Jakarta) and the Indonesian army. The protocol will require appropriate ethics committee approval.
- Approximately 150 subjects will be enrolled from the Indonesian army returning from deployment in a heavily malarious region of Indonesia (e.g. Papua) and diagnosed with *P. vivax* malaria based on microscopic examination (confirmed by a second microscopist).
- Informed consent process: Research team leaders will meet commanders and the troops to explain the concept and importance of voluntary informed consent prior to inviting subjects to participate in the study. Subjects will give written informed consent prior to any screening assessments being undertaken. The written consent will be obtained by a site team member who is independent of the subject (i.e. not the subject’s commander or supervisor) and the voluntary nature of the study will be emphasised (See Section 7.2).
- At Day 1, subjects will be screened for G6PD deficiency using a suitable Point of Care Test (e.g. Fluorescent Spot Test) in order to exclude those who are G6PD deficient (See Study Reference Manual, SRM). G6PD deficiency will also be assessed by a quantitative spectrophotometric assay but the results will not be available at the time of randomization. If results are discordant, the subject will be reviewed and appropriate G6PD testing will be repeated.
- Subjects who have undergone screening and meet the label requirements for DHA-PQP dosing can receive open label DHA-PQP if the clinician deems that appropriate and at least 3 hours have elapsed since last food intake. Thus, DHA-PQP may be commenced whilst the results of the hematology, clinical chemistry or G6PD deficiency screening tests are pending. Once all laboratory evaluations are available and subject eligibility is confirmed, they will be randomized to blinded study treatment on a 1:1:1 basis. The first dose of blinded study treatment will be administered with food at least 3 hours after dosing with DHA-PQP, on Day 1 or Day 2 (see Section 7.2).

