#### Justification of primaquine dose

Subjects in the PQ treatment arm will receive a 15mg dose of PQ for 14 days (equivalent to 0.25mg/kg in a 60kg subject), in line with the local treatment guidelines [Kusriastuti, 2012]. Subjects who have a recurrence of *P. vivax* during the study will be treated with an ACT plus PQ 0.5mg/kg for 14 days (equivalent to 30mg in a 60kg subject), which is in line with local treatment guidelines for *P. vivax* relapse.

Mild gastrointestinal upset occurs in about 10% of subjects taking PQ on an empty stomach, is dose-related and is improved by dosing with food [Fryauff, 1995]. Red cell hemolysis and methemoglobinemia are the two main hematological toxicities associated with PQ (Primaquine SmPC). Routine blood examinations (including blood cell counts and hemoglobin determinations) will be performed in line with the prescribing information. Acute hemolysis can occur if PQ is given to subjects with G6PD deficiency. All subjects who are G6PD deficient at screening will be excluded from this study. An independent assessor will determine methHb levels in order to avoid any potential for unblinding due to the anticipated increases in methHb following 8-aminoquinoline dosing (refer to SRM).

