#### 4.6.1. Risk Assessment

Potential Key Risks of Clinical Significance	Summary of Data/Rationale for Risk	Mitigation Strategy
Study Treatments		
Hemolysis in G6PD-deficient subjects	Tafenoquine and primaquine are 8-aminoquinolines, a class of drug known to exert oxidative effects on hemoglobin (Hb). In patients with G6PD deficiency (or other disorders of erythrocytic pentose phosphate pathway of glucose metabolism) hemolysis is expected due to red blood cells (RBCs) lack of capacity to protect itself against oxidative effects of such drugs. Hemolysis has been reported in G6PD deficient patients inadvertently recruited into previous TQ studies.	
 
• All subjects who are G6PD deficient will be excluded. Subjects with Hb levels <8g/dL will also be excluded.
 
• Hematological study treatment stopping criteria are provided.
 
• Subjects will be closely monitored around the expected time of Hb drop to enable intervention if required.
 
• Recommendations for clinical management of hemolysis will be provided as part of the investigator training.
 

Methemoglobinemia	
Methemoglobinemia has been observed in previous studies associated with larger total doses of tafenoquine than are being considered for clinical investigation. Risk factors have been assessed and include a strong relationship between methHb development, tafenoquine dose, and body surface area.
 
The 300mg dose recommended for this study should pose minimal risk of causing elevations of methHb of clinical concern.
 
Methemoglobinemia has also been observed following administration of large doses of primaquine and in NADH methemoglobin reductase deficient individuals.
	
 
• MetHb percentage will be monitored non-invasively at selected times throughout the study.
 

Potential Key Risks of Clinical Significance	Summary of Data/Rationale for Risk	Mitigation Strategy

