### 6.1. Treatment Assignment

Subjects will be assigned to one of three blinded treatment arms: DHA-PQP alone, DHA-PQP plus TQ or DHA-PQP plus PQ in accordance with the randomization schedule generated by Clinical Statistics, prior to the start of the study, using validated internal software.

Subjects will be randomized via an interactive web recognition system (IWRS) to blinded study treatment after beginning administration of open label DHA-PQP. Each subject scheduled to receive blinded study treatment will receive a treatment allocation number (i.e. randomization number) via the IWRS system on Day 1. The treatment allocation

ratio will be 1:1:1. Once a randomization number has been allocated to a subject, it cannot be re-assigned to any other subject.

Open label DHA-PQP will be administered daily over three consecutive days. Each dose will be taken at least 3 hours after the last food intake and no food will be taken for 3 hours after each dose. If a subject vomits within 30 minutes of taking DHA-PQP on Days 1 to 3, the whole dose should be re-administered; if the subject vomits within 30-60 minutes, half the dose should be re-administered. Repeat dosing with DHA-PQP should not be attempted more than once. If the repeat dose is vomited on Day 1, the subject should be withdrawn from the study and given appropriate rescue medication as outlined in Section 6.9.1.2.

Blinded study treatment will be administered daily over 14 days together with food (at least 3 hours after dosing with DHA-PQP on Days 1, 2 and 3). If the subject vomits within 1 hour following dosing, a repeat dose should be given. If the repeat dose is vomited on Day 1, the subject should be withdrawn from the study and given appropriate rescue medication as outlined in Section 6.9.1.2.

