#### **6.9.1.2. Rescue Medication**

Subjects diagnosed with *P. vivax* relapse (i.e. a positive blood smear with or without vivax symptoms) during the 180 day follow up period will be given an ACT plus PQ 0.5mg/kg for 14 days as rescue medication. These subjects will continue to be monitored for safety and efficacy at all scheduled visits through Day 180. Details of rescue medication including reason for the rescue medication will be recorded in the eCRF. Rescue medication will be sourced locally.

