- Methemoglobin levels will be assessed using a non-invasive machine. This assessment will be performed by an independent person who will not participate in any other study procedures at the site. The data will be transmitted securely to GSK data management and will not be shared with other site staff unless result is above a preset threshold that requires a safety assessment (refer to SRM).
- A12 lead ECG will be performed with the subject in a semi-supine position having rested in this position for at least 10 minutes beforehand. Measurements that deviate substantially from previous readings will be repeated immediately. Three (3) measurements will be taken at screening, five minutes apart.
  - The mean heart rate, RR interval, QRS duration, uncorrected QT interval and QTcF (QT corrected by Friderica's formula) will be calculated from automated ECG readings and abnormal findings will be recorded in the eCRF. The mean value recorded pre-DHA-PQP will be classified as baseline.
- A blood sample will be collected for CYP2D6 genotyping and possible G6PD genotyping. The extracted nucleic acid sample for G6PD genotyping will be stored and may be analyzed in the event of an SAE due to hemoglobin decline where a repeat G6PD phenotype assay would not define G6PD status (e.g. transfusion given or high reticulocyte count).
- Subjects who have undergone screening and meet the label requirements for DHA-PQP dosing can receive open label DHA-PQP if the clinician deems that appropriate (e.g. symptomatic disease), and at least 3 hours have elapsed since last food intake. Thus, DHA-PQP may be commenced whilst the results of the hematology, clinical chemistry or G6PD deficiency screening tests are pending. Once these laboratory test results are available and the subject eligibility is confirmed, they will be randomized via the IWRS to blinded study treatment. The first dose of blinded study treatment will be administered with food at least 3 hours after DHA-PQP on Day 1 or Day 2.

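### A man who vomits the repeat DHA-PQP dose on Day 1 is directed to rescue primaquine 0.5 mg/kg for 14 days with no G6PD condition, although his G6PD result may still be pending

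*Protocol*

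**What the plan says.** Section 6.1 of the protocol sets the vomiting rule for open-label DHA-PQP. It reads "Repeat dosing with DHA-PQP should not be attempted more than once. If the repeat dose is vomited on Day 1", and continues that "the subject should be withdrawn from the study and given appropriate rescue medication as outlined in Section 6.9.1.2".

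Section 6.9.1.2 covers men diagnosed with *P. vivax* relapse during the 180-day follow-up. They "will be given an ACT plus PQ 0.5mg/kg for 14 days as rescue medication". No other regimen is given there, and G6PD is not mentioned.

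On timing, Section 7.2 says "DHA-PQP may be commenced whilst the results of the hematology, clinical chemistry or G6PD deficiency screening tests are pending"; the synopsis and Section 4.1 say the same. The G6PD check comes later. Section 4.1 says: "Once all laboratory evaluations are available and subject eligibility is confirmed, they will be randomized to blinded study treatment".

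On the hazard, Section 4.5 states: "Acute hemolysis can occur if PQ is given to subjects with G6PD deficiency". The first mitigation listed for haemolysis in Section 4.6.1 is "All subjects who are G6PD deficient will be excluded".

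**The concern.** The rescue regimen was written for men who relapse after randomization. They have already passed the qualitative G6PD test, so Section 6.9.1.2 had no need to repeat the condition. Section 6.1 applies the same regimen to a man on Day 1 who may not have reached that check. The protocol's main control against 8-aminoquinoline haemolysis, exclusion of G6PD-deficient men, takes effect at randomization. The cross-reference bypasses it.

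At stake is the safety of an individual man: possible acute haemolysis from a 14-day primaquine course given without a known G6PD result. The trial's inference is not at stake. A man withdrawn before randomization is a screen failure (Section 5.3) and is outside the ITT, mITT and Safety populations.

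**Working it through.** No statistical figure bears on this point. The check traces the rules in order, then does the dose arithmetic.

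**Order of events on Day 1**

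| Step | Source | G6PD result required? |
|---|---|---|
| G6PD sample taken before DHA-PQP | 7.2(a), 7.1 | – |
| First DHA-PQP dose | 4.1, 7.2 | No, may be pending |
| Vomits within 60 minutes and is re-dosed in full or half | 6.1 | No |
| Vomits the repeat dose: withdrawn, sent to 6.9.1.2 | 6.1 | No |
| ACT plus primaquine 0.5 mg/kg for 14 days | 6.9.1.2 | No |
| Randomization and first blinded dose, at least 3 hours after DHA-PQP | 4.1, 6.1, 7.2 | Yes |

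If re-dosing is prompt, the man reaches the rescue instruction before the earliest possible blinded dose. That is the period in which the protocol allows results to be outstanding. His haematology may also be pending, so the exclusion for haemoglobin below 8 g/dL may not yet have been applied.

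**Do the other haemolysis controls in Section 4.6.1 cover him?**

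- The stopping criteria in Section 5.4.2 stop blinded study treatment. They do not mention rescue primaquine.
- The Time and Events table schedules haematology on Days 3, 5, 7 and 14. A man who is withdrawn and never randomized no longer has these four checks. A Withdrawal visit with haematology (Sections 5.4 and 7.1) and SAE reporting remain.

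**Dose**

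Section 4.5 gives the rescue course as "ACT plus PQ 0.5mg/kg for 14 days (equivalent to 30mg in a 60kg subject".

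- Rescue: 0.5 mg/kg × 60 kg = 30 mg/day; 30 × 14 = 420 mg.
- Blinded primaquine arm: 15 mg/day × 14 = 210 mg.
- Ratio: 420 / 210 = 2.0.

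So the man with the weaker G6PD safeguard is directed to twice the primaquine of the trial arm.

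**How many men**

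The documents give only the planned number screened, about 200. The three rates below are assumptions, and the calculation treats every such man as receiving primaquine before his result.

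| | Low | High |
|---|---|---|
| Vomits the repeat dose | 0.5% | 2% |
| Result pending at that point | 10% | 100% |
| G6PD deficient | 2% | 10% |

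- Low: 200 × 0.005 × 0.10 × 0.02 = 0.002 men.
- High: 200 × 0.02 × 1.00 × 0.10 = 0.4 men.

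**The case against.** The strongest reply is that no clinician would follow the text this way. Section 6.1 says the rescue medication must be *appropriate*, and a man who vomits on Day 1 has not relapsed, so the regimen fits him poorly on its face. The G6PD sample has already been drawn, and eligibility rests on an on-site point-of-care test. Neither section says when primaquine must start, so a result pending when he vomits may be available before the first primaquine tablet. Men with severe vomiting are excluded, early DHA-PQP is discretionary, and investigators are warned of haemolysis throughout and trained on it. The SAP (Section 2.1) also records that 150 participants had been randomised, the protocol maximum, so an amendment would not protect anyone at Day 1 in this trial.

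Most of this stands as an argument that the event is rare. The illustrative range spans 200-fold and stays below one man, and its upper end needs every result to be pending. The four lost haematology checks are context only: they follow from withdrawal, and the fix does not restore them.

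It does not supply the missing condition. *Appropriate* is followed by a pointer to a section with a single regimen. The references to local treatment guidelines (Sections 4.4 and 5.4) concern recurrence and name no G6PD test, and Section 4.4 says that facilities for G6PD testing are lacking in practice. No other sentence in the protocol makes rescue primaquine conditional on G6PD.

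**Conclusion.** The concern holds. As written, Section 6.1 can send a man of unknown or deficient G6PD status to a primaquine course with no stated check, at twice the total dose of the blinded arm in the protocol's 60 kg example. The conclusion rests on the text alone.

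The size is small. The expected number of deficient men cannot be derived from the documents and is probably well below one; the 0.002 to 0.4 range depends wholly on assumed rates. The second vomiting sentence in Section 6.1, for blinded treatment, uses the same wording but is sound, because those men were randomized after a G6PD-normal test. Sample size and primary analysis are unaffected. The rule should be corrected because the possible harm is serious and the correction is cheap.

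**What to change.** In the DHA-PQP sentence of Section 6.1, replace the pointer to Section 6.9.1.2 with a separate rule, for example:

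> If the repeat dose is vomited on Day 1, withdraw the subject and start alternative blood-stage treatment at once. Give primaquine only when a G6PD-normal result and the outstanding eligibility laboratory results are available.

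Leave the blinded-treatment sentence and Section 6.9.1.2 as they are.

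The cost is one sentence in an amendment and no added assessments. These few men would wait a little longer for primaquine, normally until Day 1 or 2, because blinded dosing on Day 1 or 2 already depends on the same results. Blood-stage treatment, the urgent part, is not delayed.

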#### **Premature Study Withdrawal**

A subject is considered to be withdrawn prematurely from the study if they do not complete the Day 180 assessment. Subjects may be prematurely discontinued from the study for any of the following reasons:

- Adverse event
- Protocol deviation
- Study closed/terminated

- Loss to follow-up
- Consent withdrawal
- Subject or investigator non-compliance
- At the request of the subject, investigator, or sponsor

Subjects are not obligated to state the reason for withdrawal from this study. However, the reasons for withdrawal, or failure to provide a reason, must be documented by the investigator on the Completion/Withdrawal section of the electronic Case Record Form (eCRF). If a subject is withdrawn from the study for any reason, the investigator should make every effort to perform the study evaluations as specified in the Time and Events table for the Withdrawal visit as applicable.

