### **Premature Withdrawal of Study Treatment**

If a subject prematurely discontinues from study treatment for any reason or reaches the primary endpoint of relapse, they should continue to attend study visits to Day 180. The reason for withdrawal from treatment should be recorded in the electronic case record form (eCRF). Given the long half life of tafenoquine, the maximal pharmacodynamic effects such as potential hemolysis or methemoglobinemia may occur several days after completion of dosing. These data will be recorded, as they comprise an essential evaluation that needs to be done before discharging any subject from the study. Therefore, the investigator should continue following subjects for all protocol assessments, up to and including Day 180 whenever possible. The subject should be given appropriate rescue therapy according to local treatment guidelines if they develop a malarial recurrence (see Section 6.9.1.2).

Subjects should discontinue taking study treatment if they meet **any** of the criteria below:

- Intolerable AEs:
  - Any grade 4 AE or toxicity in the absence of compelling evidence that the AE is not related to investigational product(s)
- Clinically significant laboratory results considered by the investigator to warrant withdrawal from the study treatment
- Liver chemistry stopping criteria (refer to Section 5.4.1 and Section 12.2 Appendix 2)
- Hemoglobin stopping criteria: Given the hemolytic potential of TQ and PQ in subjects with G6PD deficiency, study specific hematologic stopping criteria will be employed (refer to Section 5.4.2)
- QTc stopping criteria (refer to Section 5.4.3)

When QT or hemolytic stopping criteria are met, this must be promptly reported by the investigator to GSK as a Serious Adverse Event (see Section 7.5)

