#### 7.5.1.1 Protocol-Defined SAE (Hb drop)

A Hb drop is defined as any ONE of the following occurring in the first 15 days of the study:

- a relative hemoglobin decrease of  $\geq 30\%$  from baseline, *or*
- an absolute hemoglobin decrease of  $>3\text{g}$  from baseline, *or*
- a drop in absolute hemoglobin to  $< 7.0\text{g/dL}$ .

All protocol-defined Hb drops must be reported as an SAE, even if asymptomatic and not requiring medical intervention.

If a protocol-defined SAE (Hb drop) is noted, hematology and clinical chemistry tests will be performed immediately and subjects will be required to have a repeat G6PD quantitative phenotype test to confirm they are not G6PD deficient (refer to Section 5.4.2).

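### Protocol Section 6.1 withdraws from the study a randomized subject who vomits the repeat blinded dose on Day 1, although Section 5.4 keeps anyone who stops study treatment in visits to Day 180

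*Protocol*

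**What the plan says.** Protocol Section 6.1 (Treatment Assignment) deals with vomiting within an hour of the blinded dose: "a repeat dose should be given. If the repeat dose is vomited on Day 1, the subject should be withdrawn from the study". The subject then receives rescue medication, for which 6.1 refers to Section 6.9.1.2. Randomization precedes the first blinded dose, so the rule applies to a randomized subject who has taken blinded drug twice.

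Protocol Section 5.4 separates leaving the study from stopping study treatment. For a subject who stops treatment for any reason, or who relapses, "they should continue to attend study visits to Day 180". The reason given is tafenoquine's long half-life: "the maximal pharmacodynamic effects such as potential hemolysis or methemoglobinemia may occur several days after completion of dosing". The section treats these data as essential before any subject is discharged.

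For a subject who leaves the study, Section 5.4 asks the investigator only to make every effort to "perform the study evaluations as specified in the Time and Events table for the Withdrawal visit".

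Section 6.9.1.2 says of rescued subjects: "These subjects will continue to be monitored for safety and efficacy at all scheduled visits through Day 180". That sentence concerns subjects diagnosed with *P. vivax* relapse.

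**The concern.** The two sections send the same subject in opposite directions. A site that follows the specific instruction in 6.1 discharges a man whom 5.4 would keep. He may have absorbed part of two blinded doses, and the blind means the site cannot tell whether they were tafenoquine, primaquine or placebo. This is the situation for which 5.4 requires continued observation.

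What is at stake is his safety record. Section 7.5.1.1 makes a protocol-defined hemoglobin drop, "occurring in the first 15 days of the study", reportable as an SAE even when it causes no symptoms. A drop without symptoms is found only by measuring hemoglobin, and the scheduled measurements are what withdrawal removes. If a vomited dose counts as a dose received, he stays in the Safety population, and in the mITT population if parasitaemic at baseline (SAP Section 4), with almost no data after Day 1.

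There is also a gap. The rule names only Day 1, while blinded treatment may start on Day 2. Day 1 may be shorthand for the first blinded dosing day, as the footnote to Figure 1 suggests, but 6.1 does not say so.

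**Working it through.** **1. The two rules compared**

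| | Section 6.1 | Section 5.4 |
|---|---|---|
| Trigger | Repeat blinded dose vomited on Day 1 | Study treatment stopped for any reason |
| Consequence | Leaves the study, given rescue | Visits continue to Day 180 |
| Reason given | None | Hemolysis or methemoglobinemia may peak days later |

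Stopping blinded treatment because of vomiting falls within any reason. Neither section refers to the other on this point.

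**2. Scheduled assessments lost by withdrawal on Day 1** (Protocol Sections 7.1, 7.4, 7.5.4 and 7.5.5)

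- Hematology: Days 3, 5, 7, 14, 21, 28, 60, 90, 120 = 9 visits. Days 3, 5, 7 and 14 = 4 fall within the first 15 days.
- Methemoglobin: daily on Days 2-14 = 13; alternate days read as 16, 18, ..., 28 = 7; Day 60 = 1. Total 13 + 7 + 1 = 21.
- ECG: Day 3 (before and 4 hours after the last DHA-PQP dose), Day 7 and Day 28.
- Smears: the Day 2-3 clearance smears, then Days 7, 14, 21, 28, 60, 90, 120, 150, 180 = 9.

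Against this he gains one withdrawal visit, on a best-effort basis.

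**3. Effect on the primary analysis**

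The plan's power figure comes first. Inputs from Protocol Section 9.2.1: 50 per group, 10% withdrawal, relapse-free efficacy 50% against 85%; two-sided 5% from Section 9.1.

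- Evaluable per arm: 50 × 0.9 = 45.
- Two proportions, normal approximation: 95.6%.
- Log-rank: hazard ratio ln(0.85)/ln(0.50) = 0.234; events 45 × (0.50 + 0.15) = 29.25; power 97.5% (Schoenfeld) or 91.8% (Freedman).

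All agree with the stated figure of more than 90%. Removing a further 1, 2, 3 or 5 tafenoquine subjects at time zero gives 95.4%, 95.2%, 95.0% or 94.4% (two proportions).

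Even that small loss is not caused by 6.1. Under SAP Section 11.6.3, a subject who starts another antimalarial before any negative smear is censored at 0 days, so keeping him in visits does not change his contribution. The exception is a later relapse: the SAP lets a relapse override censoring, and only a subject still being followed can be seen to relapse. This assumes that rescue is classed as a concomitant antimalarial.

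**4. Number of subjects**

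The documents give no rate of repeat vomiting. Assuming 0.5% to 3% of 150: 150 × 0.005 = 0.75 and 150 × 0.03 = 4.5, over all three arms. The true number could be zero.

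**The case against.** The strongest reply is that 6.1 is a specific rule beside a general one. Section 5.4 allows withdrawal from the study for safety or administrative reasons and qualifies continued follow-up by what is possible, so 6.1 may be a deliberate Day 1 exception. That reading is available, but no reason for an exception is given, and effective treatment does not require ending follow-up. Rescue and visits can go together.

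Cover also remains after withdrawal. SAEs and adverse events of special interest are followed to resolution (7.5.1.4), clinically significant laboratory abnormalities are repeated until they settle (7.5.5), and the clinic on the base is open at all hours. This stands and reduces the size of the problem. It does not find a symptomless hemoglobin drop that nobody measures. Many of the lost visits, from Day 60 on, have little to do with late hemolysis; the early ones matter most.

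Two stronger readings are tempting, and the documents do not support them.

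- A reader might infer that 6.1 also contradicts 6.9.1.2. The Day 180 sentence there covers relapsers, and a Day 1 vomiter has not relapsed. It supports retention only indirectly, through the cross-reference from 6.1.
- A reader might infer that the main harm is unmonitored high-dose primaquine. A subject rescued under 6.9.1.2 "will be given an ACT plus PQ 0.5mg/kg for 14 days as rescue medication". Section 4.5 describes the daily dose as "equivalent to 30mg in a 60kg subject", so 30 × 14 = 420 mg against 15 × 14 = 210 mg in the primaquine arm. But 6.1 asks only for appropriate rescue, and this dose is written for relapse. The protocol also gives every non-relapser the same course at Day 180, and the Day 195 visit has no hemoglobin or methemoglobin check (Sections 6.8 and 7.1). Rescue primaquine alone therefore cannot carry the safety argument.

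**Conclusion.** Sections 6.1 and 5.4 contradict each other for a randomized, dosed subject who vomits the repeat blinded dose on Day 1. For each such subject, 6.1 costs the assessments counted above, of which the four early hematology visits are the most important. The argument rests on the reason 5.4 itself gives for continued observation and on the 15-day hemoglobin window.

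The severity is minor. The number affected is unknown and probably small; the range shown is an assumption. The effect on the primary analysis is negligible, and no direction of bias is claimed. A reader might infer that the rule distorts the treatment comparison, but the SAP's censoring rule gives the same result for a non-relapsing subject whether he is kept or withdrawn.

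**What to change.** In the blinded-dose sentence of Section 6.1, replace *withdrawn from the study* with *withdrawn from study treatment, given appropriate rescue, and followed to Day 180 per Section 5.4*. State that this applies to the first day of blinded dosing, Day 1 or Day 2. Make the same change in the DHA-PQP sentence for any subject already randomized and dosed. That case should be rare, because blinded drug is given at least 3 hours after DHA-PQP and subjects never randomized are screen failures (Section 5.3).

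As a minor conforming edit, change *discontinued from the study* in the triplicate-ECG example of Section 5.4.3 to *discontinued from study treatment*, in line with that section's opening.

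The cost is a few words, since the visits are already scheduled. The change helps only subjects not yet dosed, and SAP Section 2.1 records that 150 participants had been randomized. From then on, the planned outputs are enough to show whether the rule was used: per-protocol exclusion 02 with Table 1.12, Tables 1.1, 1.2 and 1.32, and the exposure listing (shell EX3). No new table is needed.
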